15.3 Fatal Overdose

We will collect data on fatal overdoses using medical chart record review at 16 weeks for participants who are lost to follow-up. We will supplement this with information from contacts with persons listed on the participant's locator form when participants are lost to follow-up throughout the study. If a fatal overdose occurred, the event also should be captured on the AE/SAE CRF.

15.4 Precipitated Withdrawal

For participants assigned to XR-NTX, the study clinician will record the presence or absence of precipitated opioid withdrawal following each XR-NTX injection.

16.0 STUDY CONDITIONS

The two study conditions are: 1) office-based XR-NTX, and 2) TAU. Study conditions are discussed in detail in section 4.2, 4.3, and 9.0.

16.1 Clinic-Based XR-NTX

The office-based XR-NTX study condition is discussed in detail in Sections 4.2 and 9.0.

16.2 TAU

The TAU study condition is discussed in detail in Sections 4.3 and 9.0.

16.3 Training

Training in study-specific assessments will be provided as specified in a comprehensive training plan that will be developed by EMMES, the Lead Team, and other participating nodes. The trainings will include modules targeting all research team members conducted via web, telephone and in-person training sessions. Training will cover standard NIDA training for all CTN Trials (e.g., Good Clinical Practices), as well as protocol specific training as needed (e.g., assessments, study intervention, fidelity to the protocol, safety procedures, data management and collection, research procedures). Attention will be given to provide the study clinic staff providers training in management of opioid and alcohol withdrawal, XR-NTX induction and maintenance, and to familiarize study personnel with study procedures. Support mechanisms are identified (e.g., who to contact for aid, questions, resources) as well as re-training procedures. All study staff will be required to complete any local training requirements per study site and IRBs. Further details are presented in the study Training Plan located in the Operations Manual.

16.4 Concomitant Medications

Participants will be instructed to contact the study medical clinician if they plan on taking any concomitant medications (including prescription, over-the-counter, and herbal supplements) during the course of the study.

As described in the eligibility criteria, participants will be excluded if there is a need for ongoing opioid analgesic treatment. The study medical clinician may also exclude any participant taking medications that could interact adversely with study drugs at his/her clinical discretion.

Study screening and treatment induction procedures (requirement for negative UDS for opioids on day of induction) are anticipated to greatly decrease the risk of precipitating opioid withdrawal. In the event a participant experiences opioid withdrawal following XR-NTX injection, the study clinician may dispense symptomatic treatments (e.g. oral clonidine, prochlorperazine, ibuprofen, etc.) to alleviate symptoms of opioid withdrawal, according to local SOPs. XR-NTX can also be associated with transient nausea unrelated to opioid withdrawal, typically lasting 2-8 hours. Should participants develop nausea or vomiting during naltrexone induction, this will be treated with oral anti-emetics such (e.g. prochlorperazine) as needed.

17.0 STATISTICAL ANALYSIS

Primary Objective of the Analysis:

The Primary Objective of the CHOICES pilot study is to determine the acceptability and feasibility of XR-NTX in HIV practice and inform development of a multi-site comparative effectiveness trial of XR-NTX vs. TAU in HIV clinics.

17.1 Primary Outcome Measures

Primary outcome variables for the CHOICES pilot study are:

- 1) HIV provider willingness to prescribe XR-NTX (Aim 1): HIV provider willingness to prescribe opioid antagonist treatment will be assessed with measures adapted from the Medical Opinion Survey (MOS) in the provider survey (mean; survey data).
- 2) Patient acceptance of opioid antagonist therapy (Aim 2): HIV-infected patient acceptance of opioid antagonist treatment will be assessed with measures adapted from the Medical Opinion Survey (MOS), administered during participant recruitment. Patients will be asked whether they are willing to participate in a trial of XR-NTX vs. TAU (binary; survey data).
- 3) Rate of participant recruitment into trial (Aim 3): Number of participants randomized in pilot study per 12 months. This will be used to estimate the speed at which a multisite trial could enroll participants. The number of participants randomized will be assessed on a monthly basis until either 50 participants have enrolled, or 12 months of recruitment have elapsed, whichever comes first (rate; randomization data).
- 4) Treatment initiation (Aim 4A): Treatment initiation is defined as receipt of at least one dose of study medication for those randomized to XR-NTX within 4 weeks of randomization. For those randomized to TAU, treatment initiation will be defined as receiving at least one dose of medication-assisted therapy other than XR-NTX (e.g., buprenorphine for opioid use disorder, disulfiram for alcohol use disorder), or attendance on at least 1 day of non-medication-assisted therapies (e.g., 12-step groups, outpatient rehab referral, etc.) within 4 weeks of randomization. Treatment initiation will be assessed with weekly phone calls from research staff until treatment is initiated or 4 weeks from date of randomization have elapsed, as which point a participant will be considered to have failed treatment initiation. (binary; chart review and self-report).
- 5) Retention on treatment (Aim 4B): Retention on treatment is defined as the percent of assigned treatment received over 16 weeks after randomization. Only participants who initiate treatment (as defined in Aim 4A) will be assessed for retention on treatment. Retention will be assessed by the study clinician at 4, 8, 12, and 16 weeks following treatment initiation. For those randomized to XR-NTX, retention on treatment is defined as the mean percent of expected XR-NTX doses received (25%, 50%, 75%, or 100% of 4 possible doses). For those randomized to TAU, study clinicians will estimate the percent of recommended treatment a participant received in the past 4 weeks at weeks 4, 8, 12, and 16. Retention on treatment for TAU is defined as the mean percent of recommended TAU treatment received (1-100% possible range), as estimated by the study clinician. (percent; chart review and self-report).

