Aim 4: Assess the feasibility of integrating XR-NTX for opioid and alcohol use disorders into HIV clinics. Data collection during study start-up will inform selection of 2 HIV clinics to implement XR-NTX treatment. HIV providers and staff will be trained in detoxification and XR-NTX induction and management. HIV-infected subjects with untreated opioid and/or alcohol use disorders will be randomized to XR-NTX or TAU, followed by detoxification (if needed) and treatment induction. The primary outcomes are 1) treatment initiation (successful treatment initiation of XR-NTX or TAU within 4 weeks of randomization), and 2) retention on treatment condition at 16 weeks. Secondary outcomes include change in 1) HIV-1 RNA viral suppression, 2) Illicit drug and alcohol use, 3) HIV care engagement (receipt of ART, HIV visit adherence, ART adherence), and safety (percent with precipitated withdrawal, hepatotoxicity, or overdose).

Aim 4 Pilot Objective A: Estimate effect size point estimates for rate of treatment initiation and 16 week retention among HIV-infected patients with alcohol or opioid use disorders randomized to XR-NTX vs. TAU.

Aim 4 Pilot Objective B: Estimate effect size point estimates for secondary outcomes of HIV-1 RNA viral suppression, illicit drug and alcohol use, HIV care engagement, and safety among HIV-infected patients with alcohol or opioid use disorders randomized to XR-NTX vs. TAU.

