8.0 OUTCOME MEASURES

8.1 Primary Outcome Measures

Primary outcome variables for the CHOICES pilot study are:

- 1) HIV provider willingness to prescribe XR-NTX (Aim 1): HIV provider willingness to prescribe opioid antagonist treatment will be assessed with survey measures adapted from the Medical Opinion Survey (MOS) during the study start-up period (mean; survey data).
- 2) Patient acceptance of opioid antagonist therapy (Aim 2): HIV-infected patient acceptance of opioid antagonist treatment will be assessed with measures adapted from the Medical Opinion Survey (MOS), administered during participant recruitment. Patients will be asked whether they are willing to participate in a trial of XR-NTX vs. TAU (binary; survey data).
- 3) Rate of participant recruitment into trial (Aim 3): This will be used to estimate the speed at which a multisite trial could enroll participants. The number of participants randomized will be assessed on a monthly basis until either 50 participants have enrolled, or 12 months of recruitment have elapsed, whichever comes first (rate; randomization data).
- 4) Treatment initiation (Aim 4A): Treatment initiation is defined as receipt of at least one dose of study medication for those randomized to XR-NTX within 4 weeks of randomization. For those randomized to TAU, treatment initiation will be defined as receiving at least one dose of medication-assisted therapy other than XR-NTX (e.g., buprenorphine for opioid use disorder, disulfiram for alcohol use disorder), or attendance on at least 1 day of non- medication-assisted therapies (e.g., 12-step groups, outpatient rehab referral, etc.) within 4 weeks of randomization. For the TAU group, treatment initiation will be assessed with weekly phone calls from research staff until treatment is initiated or 4 weeks from date of randomization have elapsed, as which point a participant will be considered to have failed treatment initiation (binary; chart review and self-report).

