9.3 Treatment Conditions

9.3.1 HIV Usual Care (Both Arms)

All participants receive comprehensive HIV primary care, case management, addiction counseling, and social support services from HIV clinics as they would regardless of study participation. As part of protocol training, HIV clinic providers will be encouraged to offer ART within 4 weeks of randomization for participants not already prescribed ART. Current guidelines recommend offering ART to all HIV-infected participants, regardless of CD4 count (Thompson, Aberg et al. 2012). The schedule of medical care provided will be as deemed appropriate by the treating provider. HIV-infected participants are typically seen at least twice within the first month of initiating ART, and at least every 3 months thereafter for monitoring. Medical visits will not be considered study visits, though they may coincide with study visits. HIV clinic treatment will also include usual addiction counseling services, which are offered as a part of usual care in most large U.S. HIV clinics. As part of protocol training, HIV clinic providers will be asked to refer study participants to existing addiction counseling services in their clinic, as they would do regardless of study participation. Throughout the course of the trial, HIV clinics will be monitored for any potential changes that might occur in standard practice around medical management of HIV infection or addiction treatment services. HIV clinic medical and counseling visits will be tracked through medical record abstraction throughout study participation (See Section 10 Assessments).

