9.3.3 Clinic-based Extended-Release Naltrexone (XR-NTX)

9.3.3.1 XR-NTX Detoxification and Induction (0 - 4 weeks duration)

Following randomization, participants assigned to office-based XR-NTX will undergo detoxification and naltrexone induction in accordance with published guidelines (Asplund, Aaronson et al. 2004; Mayo-Smith, Beecher et al. 2004; Center for Substance Abuse Treatment 2006; Sigmon, Bisaga et al. 2012). Participating HIV providers will be trained to assess potential participants for the anticipated severity of opioid and alcohol withdrawal symptoms and manage outpatient detoxification procedures for participants with mild to moderate anticipated opioid or alcohol withdrawal severity. Participants with anticipated severe withdrawal symptoms (e.g., > 6 bags per day of heroin; >100 mg/day morphine equivalents prescription opioid use) will be referred to local detox facilities for medication-assisted inpatient detoxification that may involve opioid medications. Participants with anticipated severe alcohol withdrawal (increased risk of delirium tremens, seizures) should be admitted for inpatient detoxification. Guidelines for detoxification and induction onto XR-NTX are provided in study SOPs.

Prior to the naloxone challenge, participants randomized to XR-NTX must complete/have completed opioid detoxification, be at least 24 hours removed from the last dose of opioid agonist (heroin, prescription opioids, methadone or buprenorphine) and have a UDS negative for the extended opioid spectrum. If initial UDS is positive, UDS is repeated daily until negative. Only then will the naloxone/ challenge take place.

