9.3.4 Treatment as Usual (TAU)

Participants assigned to the TAU group will receive the standard treatment for alcohol and opioid use disorders provided at each HIV clinic. The standard of care in U.S. and Canadian HIV clinics is currently to link with opioid agonist treatment services. Opioid substitution therapy is recommended for HIV-infected participants with opioid dependence (Thompson, Aberg et al. 2012; Thompson, Mugavero et al. 2012), and many HIV practices are being encouraged to adopt clinic-based BUP/NX (HIV/AIDS Bureau Special Projects of National Significance Program 2012). The standard of care for treatment of alcohol use disorders in HIV clinics is referral to detoxification, if needed, as well as outpatient or inpatient rehabilitation programs and 12-step groups, and/or on-site substance abuse counseling services. Medication-assisted treatment of alcohol use disorders with naltrexone, disulfiram, or acamprosate is rare in HIV clinics.

Many HIV clinics receive funding from the Ryan White Care Act for case management and addiction/mental health counseling services to facilitate engagement of HIV-infected patients with substance use disorders in treatment. In a 6-month randomized trial of methadone maintenance referral strategies, passive referral of heroin users resulted in 8% methadone maintenance enrollment at 6 months vs. 29% enrollment among those randomized to case-management assisted referrals ($p = .006$) (Coviello, Zanis et al. 2006).

Methadone maintenance referrals in HIV clinics may more closely approximate case-managed referral enrollment due to the presence of Ryan White Care Act-funded case managers and counselors.

During the formal site selection process, a thorough assessment will be conducted of each site's standard practice for linkage to addiction treatment services. Throughout the course of the trial, HIV clinics will be monitored for any potential changes that might occur in standard practice around linking HIV-infected clinic patients to substance use treatment.

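### The TAU rule for primary outcome 4A requires attendance but lists a referral as a qualifying example, and does not say whether detoxification-only doses count

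*Protocol*

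**What the plan says.** Treatment initiation within 4 weeks (Aim 4A) is a primary outcome, defined in Protocol 8.1 and again in 17.1. In the XR-NTX arm it requires at least one dose of study medication. In TAU either of two limbs suffices:

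- Medication limb (17.1): "receiving at least one dose of medication-assisted therapy other than XR-NTX (e.g., buprenorphine for opioid use disorder, disulfiram for alcohol use disorder").
- Non-medication limb (17.1): "attendance on at least 1 day of non-medication-assisted therapies (e.g., 12-step groups, outpatient rehab referral, etc.) within 4 weeks of randomization". Section 8.1 gives the same pair of examples: "12-step groups, outpatient rehab referral, etc.) within 4 weeks of randomization".

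The outcome is scored from chart review and self-report, with weekly calls by research staff, in a study that 9.8 describes as unblinded. Under 8.1 and 17.1, only those who meet 4A are assessed for retention (4B). The TAU retention scale there runs from 1% to 100%.

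On detoxification, Aim 4 in section 2.1 says participants "will be randomized to XR-NTX or TAU, followed by detoxification (if needed) and treatment induction". Section 9.3.3.1, on the XR-NTX arm, says those expected to have severe withdrawal "will be referred to local detox facilities for medication-assisted inpatient detoxification that may involve opioid medications".

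**The concern.** The governing word of the non-medication limb is attendance, yet one of its two named examples is a referral. A referral is an act of the provider; it does not show that the participant received anything. Staff at two sites, both working from the protocol, could score the same referred but non-attending participant differently.

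Referral is a common route in TAU. Section 4.3 says HIV patients with alcohol use disorders are typically referred on. Section 9.3.4 describes usual alcohol care largely as referral, alongside on-site counseling.

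The medication limb has a gap of its own. It does not say whether a dose given only for detoxification is a dose of medication-assisted therapy. An XR-NTX participant who completes detoxification and receives no injection is a failure. A TAU participant given a buprenorphine or methadone dose in detoxification might be scored a success.

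Both ambiguities act in TAU only and in one direction. At stake are the TAU initiation estimate, the comparison of arms in Objective 4A, the make-up of the TAU group in 4B, and the values handed to the planned multi-site trial.

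**Working it through.** **1. The text side by side**

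| Contact within 4 weeks | XR-NTX arm | TAU arm |
|---|---|---|
| Referral issued, nothing attended | Not initiation | Fails on the word attendance; passes on the listed example |
| Detoxification only, with a medication dose | Not initiation | Not stated |
| One dose or one attended day of assigned treatment | Initiation (dose) | Initiation |

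The first two rows are where the arms can part. The example appears in both definitions, so it is not an isolated slip.

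**2. The planned precision**

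Table 17.2.1 (rate 2.28 per site-month, 2 sites, limits of 50 participants and 12 months) gives a 20th percentile of n of 48, and 80th percentiles of the 95% half-width of 0.21 for p(init) and 0.22 for p(ret).

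Check: total n = min(Poisson(2.28 × 2 × 12), 50), split 1:1, exact binomial intervals, 90% of the arm retained for p(ret), and p = 0.5 (an assumption, since the simulated value is not stated). This gives n = 48, 0.206 and 0.223. By hand for 24 per arm, 1.96 × √(0.25/24) = 0.200, and the widest exact half-width is 0.209. The plan's figures reproduce, and none of them depends on the disputed wording.

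**3. Possible size in 4A**

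Let p be the true TAU initiation probability and q the share of true non-initiators scored as initiated on a referral or detoxification contact. Then

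scored rate = p + (1 − p)q, and shift = (1 − p)q.

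Both p and q are assumptions. The ends 0.29 and 0.74 coincide with percentages quoted in 9.3.4 and 4.1 and serve only to give a wide span; they do not estimate 4-week initiation.

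| p | q = 0.1 | q = 0.2 | q = 0.3 |
|---|---|---|---|
| 0.29 | 0.361 (+0.071) | 0.432 (+0.142) | 0.503 (+0.213) |
| 0.50 | 0.550 (+0.050) | 0.600 (+0.100) | 0.650 (+0.150) |
| 0.74 | 0.766 (+0.026) | 0.792 (+0.052) | 0.818 (+0.078) |

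The shift runs from 0.26 × 0.1 = 0.026 to 0.71 × 0.3 = 0.213. In 25 TAU participants that is 0.65 to 5.3, or about 1 to 5 people.

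**4. Carry-over into 4B**

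The share of the TAU retention group who never started is (1 − p)q / [p + (1 − p)q]:

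- p = 0.74, q = 0.1: 0.026/0.766 = 3%
- p = 0.50, q = 0.2: 0.100/0.600 = 17%
- p = 0.29, q = 0.3: 0.213/0.503 = 42%

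A person who received nothing has no place on a scale that starts at 1%, so 4B presupposes that everyone entering it has had some treatment.

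**The case against.** The best defense is that attendance governs and the parenthesis only illustrates kinds of therapy, so a participant who is referred and never attends fails the rule as written. That stands. A reader might infer that the protocol counts a referral alone as initiation, but the text does not go that far. What it does is give an example that cannot meet its own requirement.

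A reader might also infer that any dose other than XR-NTX counts, detoxification doses included. The text does not say so. The limb is confined to medication-assisted therapy, and its examples are tied to treating the disorder. Elsewhere detoxification is kept apart: Aim 4 places it before induction, 13.6 lists it separately from medication-assisted services, and 19.3.2 gives detoxification admissions their own form. The phrase describing detoxification as medication-assisted sits in the XR-NTX procedure. What remains is silence on a buprenorphine or methadone dose given only for detoxification.

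A third temptation is to size the problem from the cited referral studies: "passive referral of heroin users resulted in 8% methadone maintenance enrollment at 6 months vs. 29% enrollment among those randomized to case-management assisted referrals" in 9.3.4, and 41% engagement after methadone referral in 4.1. Their complements (59% to 92%) do not measure this error. They concern methadone, which belongs to the medication limb and needs a dose there. The 8% and 29% are counted at 6 months, whereas 4A asks for one dose or one attended day within 4 weeks. Section 9.3.4 itself expects HIV clinics to be closer to the case-managed figure than the passive one. Using the complements would also assume that every unattended referral is scored as initiation.

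Two further points limit the concern. Section 9.3.1 says "HIV clinic providers will be asked to refer study participants to existing addiction counseling services in their clinic", but that applies to both arms and to in-clinic counseling, so it is weak evidence about rehabilitation referrals. Chart review, the services review in 13.6 (sessions attended) and the detoxification form should also make many referral-only and detoxification-only cases identifiable. Identifying them still does not say how to score them.

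**Conclusion.** The point holds as a contradiction and a gap in the stated scoring rule of a primary outcome. On referral, sections 8.1 and 17.1 require attendance and name an example that cannot be attended. On detoxification, TAU is left open where the XR-NTX arm is closed. Any resulting error raises TAU initiation only, moves the XR-NTX minus TAU difference down by the same amount, and puts non-starters into 4B.

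The size is not known from the documents. Under the assumed 10% to 30% misclassification of true TAU non-initiators and assumed true rates of 0.29 to 0.74, the TAU rate rises by about 3 to 21 points. The top of that range equals the planned half-width of about 21 points; most of it lies below. If every scorer applies the attendance requirement strictly and excludes detoxification doses, the shift is zero. The rule should be corrected, but it does not show that the design counts referrals.

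**What to change.** Make the same edits in 8.1 and 17.1:

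1. Replace the referral example with *outpatient rehabilitation session attended*.
2. Add: *A referral or appointment alone is not treatment initiation.*
3. Add: *Contacts or doses given only for detoxification are not treatment initiation in either arm.* This scores both arms alike and agrees with Aim 4, which places detoxification before induction.
4. Put the same three points in the script for the weekly calls.

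The cost is a few wording changes and a line in the script; no new data collection is needed. The downside is that TAU initiation may come out lower, and fewer TAU participants may enter 4B. These are scoring rules only and do not affect how any participant is treated.
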